The Yale University Principal Investigator, all Yale University co-investigators, and all Yale University individuals who are responsible for the design, conduct or reporting of research must have a current financial disclosure form on file with the University's Conflict of Interest Office. Yale New Haven Hospital personnel who are listed as con-investigators on a protocol with a Yale University Principal Investigator must also have a current financial disclosure form on file with the University's Conflict of Interest Office. If this has not been done, the individual(s) should follow this link to the COI Office Website to complete the form: http://www.yale.edu/coi/

NOTE: The requirement for maintaining a current disclosure form on file with the University's Conflict of Interest Office extends primarily to Yale University and Yale-New Haven Hospital personnel. Whether or not they are required to maintain a disclosure form with the University's Conflict of Interest Office, all investigators and individuals deemed otherwise responsible by the PI who are listed on the protocol are required to disclose to the PI any interests that are specific to this protocol.

# c. Additional Required Documents (check all that apply):

*YCCI-Scientific and Safety Committee (YCCI-SSC)	Approval Date:
*Pediatric Protocol Review Committee (PPRC)	Approval Date:
*YCC Protocol Review Committee (YRC-PRC)	Approval Date:
*Dept. of Veterans Affairs, West Haven VA HSS	Approval Date:
*Radioactive Drug Research Committee (RDRC)	Approval Date:
VNHH-Radiation Safety Committee (YNHH-RSC)	Approval Date:
Magnetic Resonance Research Center PRC (MRRC-PRC)	Approval Date:
YSM/YNHH Cancer Data Repository (CaDR)	Approval Date:

Dept. of Lab Medicine request for services or specimens form

Imaging on YNHH Diagnostic Radiology equipment request form (YDRCTO request) found at http://radiology.yale.edu/research/ClinTrials.aspx)

\*Approval from these committees is required before final HIC approval is granted. See instructions for documents required for initial submission and approval of the protocol. Allow sufficient time for these requests. Check with the oversight body for their time requirements.

2. Probable Duration of Project: State the expected duration of the project, including all follow-up and data analysis activities. 12 months

3.	Research Type/Phase: (Check all that apply)
	a. Study Type
	Single Center Study
	Multi-Center Study
	Does the Yale PI serve as the PI of the multi-site study? Yes No
	Coordinating Center/Data Management
	Other:
	b. Study Phase N/A
	Pilot Phase I Phase II Phase III Phase IV
	Other (Specify):

Page 3 of 26

- 4. Area of Research: (Check all that apply) Note that these are overlapping definitions and more than one category may apply to your research protocol. Definitions for the following can be found in the instructions section 4c:
- Clinical Research: Patient-Oriented
- Clinical Research: Epidemiologic and Behavioral
- Translational Research #1 ("Bench-to-Bedside")
- Translational Research #2 ("Bedside-to-Community")
- 5. Is this study a clinical trial? Yes 🖂 🛛 No 🗌

NOTE the current ICMJE (International Committee of Medical Journal Editors) definition of a clinical trial: "any research study that prospectively assigns human participants or groups of humans to one or more health-related interventions to evaluate the effects on health outcomes." Health-related interventions include any intervention used to modify a biomedical or health-related outcome (for example, drugs, surgical procedures, devices, behavioral treatments, dietary interventions, and process-of-care changes). Health outcomes include any biomedical or health-related measures obtained in patients or participants, including pharmacokinetic measures and adverse events" If yes, where is it registered?

Clinical Trials.gov registry  $\boxtimes$ Other (*Specify*)

## Registration of clinical trials at their initiation is required by the FDA, NIH and by the ICMJE.

If this study is registered on clinicaltrials.gov, there is new language in the consent form and compound authorization that should be used.

For more information on registering clinical trials, including whether your trial must be registered, see the YCCI webpage, http://ycci.yale.edu/researchers/ors/registerstudy.aspx or contact YCCI at [contact])

6. Does the Clinical Trials Agreement (CTA) require compliance with ICH GCP (E6)? Yes ⊠ No □

7. Will this study have a billable service? A Billable Service is defined as a service or procedure that will be ordered, performed or result in charging in EPIC for individuals who are enrolled in a clinical research study, regardless if the charge is intended to be paid by the subject/their insurance or the research study.

Yes 🛛 No

If you answered "yes", this study will need to be set up in OnCore Support http://medicine.yale.edu/ymg/systems/ppm/index.aspx

8. Are there any procedures involved in this protocol that will be performed at YNHH or one of its affiliated entities? Yes No X\_ If Yes, please answer questions a through c and note instructions below. If No, proceed to Section III.

a. Does your YNHH privilege delineation currently include the **specific procedure** that you will perform?

Page 4 of 26

 Clinical Research: Outcomes and Health Services
 Interdisciplinary Research
 Community-Based Research b. Will you be using any new equipment or equipment that you have not used in the past for this procedure?

c. Will a novel approach using existing equipment be applied?

If you answered "no" to question 7a, or "yes" to question 7b or c, please contact the YNHH Department of Physician Services ([name]) for prior approval before commencing with your research protocol.

#### SECTION III: FUNDING, RESEARCH TEAM AND TRAINING

1. **Funding Source:** Indicate all of the funding source(s) for this study. Check all boxes that apply. Provide information regarding the external funding source. This information should include identification of the agency/sponsor, the funding mechanism (grant or contract), and whether the award is pending or has been awarded. Provide the M/C# and Agency name (if grantfunded). If the funding source associated with a protocol is "pending" at the time of the protocol submission to the HIC (as is the case for most NIH submissions), the PI should note "Pending" in the appropriate section of the protocol application, provide the M/C# and Agency name (if grant-funded) and further note that University (departmental) funds support the research (until such time that an award is made).

PI	Title of Grant	Name of Funding Source	Funding	Funding Mechanism
[name], PhD	NA	departmental	
 
Federal
 
State
 
Non
 
Profit
 
Industry
 
Other
 
For Profit
 
Other
 
none
 
	Grant-M# Contract# Contract Pending Investigator/Department Initiated Sponsor Initiated Other, Specify: Yale

IRB Review fees are charged for projects funded by Industry or Other For-Profit Sponsors. Provide the Name and Address of the Sponsor Representative to whom the invoice should be sent. *Note: the PI's home department will be billed if this information is not provided.* 

# SECTION V: RESEARCH PLAN

1. Statement of Purpose: State the scientific aim(s) of the study, or the hypotheses to be tested.

To investigate the use of topical tofacitinib to promote hair regrowth in patients with alopecia areata, alopecia totalis, and alopecia universalis.

2. **Background:** Describe the background information that led to the plan for this project. Provide references to support the expectation of obtaining useful scientific data.

Alopecia areata (AA) is a condition characterized by recurrent localized hair loss, usually involving the scalp, though other hair-bearing sites may be affected. Two variants of AA, alopecia totalis (AT) and alopecia universalis (AU), are characterized by complete loss of scalp hair and complete loss of all body hair, respectively. The prevalence of AA is 0.1-0.2%; its variants occur less often. The treatment of AA includes steroid injections into the skin at sites of involvement as well as topical steroids. When these therapies fail there are few, if any, reliable treatment options.

In a murine model of alopecia areata, a Type I cytotoxic pathway has been demonstrated to be responsible for the disease state, with NKG2D-expressing CD8+ cytolytic T-lymphocytes identified as both necessary and sufficient for induction of disease. Upregulation of IL-15 in the outer root sheath of the hair follicle activates cytolytic T-lymphocytes, which in turn produce IFN, leading to activation of the hair follicle and upregulation of IL-15, NKG2D ligands, and MHC molecules, all of which target the hair follicle for attack. Systemic treatment with the JAK inhibitors tofacitinib (a JAK 1/3 inhibitor) and ruxolitinib (a JAK 1/2 inhibitor) prevents the onset of AA in grafted AA mice, and topical treatment reverses AA in these mice. JAK 1/3 signaling mediates IL-15 activation of T-lymphocytes, explaining the success of these therapies.

tofacitinib will be applied to up to half of the alopecic patches (no more than 4 patches). In participants with AT or AU, tofacitinib 2% ointment will be applied to half of the scalp. Topical tofacitinib will be applied twice daily. Patients will wash their hands prior to and following application of the ointment. Patients demonstrating hair regrowth in the tofacitinib application sites will subsequently apply tofacitinib ointment to all involved sites when evidence of regrowth is observed at the initial sites of application. Treatment will be discontinued when either full regrowth has occurred in areas of application or at 6 months of treatment, whichever comes first. If a clinically significant adverse effect (lab abnormality or patient-reported adverse effect) is encountered, then the application frequency will be decreased to once daily. In the case of a serious adverse effect, tofacitinib ointment will be immediately discontinued.

Screening labs will include *QuantiFERON®* TB gold or PPD, fasting lipid panel, complete metabolic panel, and complete blood count with differential. Females of childbearing potential will require a negative pregnancy test prior to initiating treatment. While on treatment, participants will be evaluated every 4 weeks. Physical exam of the skin with special attention to presence or absence of hair growth, photographs of the skin, as well as a complete review of systems (headache, dizziness, fever, cough, shortness of breath, nausea, vomiting, diarrhea) will be performed at each visit. Severity of Alopecia Tool (SALT) will be used to score alopecia severity prior to and at the end of treatment, and the change in SALT score will be measured. Visits will take place at Yale Dermatology – Middlebury or Yale Dermatology Associates. Patients will be evaluated monthly for a maximum of 6 months. As above, patients who experience complete hair growth prior to 6 months will discontinue therapy at the visit when full hair growth has occurred. Labs will be monitored at 1 month and at completion of therapy, which for most patients will be after 6 months of treatment, and will include fasting lipid panel, complete blood count with differential, and complete metabolic panel. This will require 2-3 vials or approximately 6-12 mL of blood at each blood draw).

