- Diagnosis of AA with at least 2 patches of alopecia involving the scalp, AT or AU
- Stable hair loss present for 6 months or longer
- No treatment for alopecia areata in the past 1 month
- No evidence of spontaneous hair regrowth

Patients will be excluded from the study if any of the following conditions are met:

- Age <18 years old
- Patients have received treatment known to affect alopecia areata within 1 month of enrolling in the study
- Patients whose current episode of AT or AU is more than 5 years
- Patients with a history of malignancy (except history of successfully treated basal cell or squamous cell carcinoma of the skin)
- Patients known to be HIV or hepatitis B or C positive

## Page 10 of 26

- Patients with positive tuberculin skin test or positive QuantiFERON® TB test
- Patients with leukopenia or anemia
- Patients with renal or hepatic impairment
- Patients taking immunosuppressive medications, including but not limited to prednisone, methotrexate, mycophenolate mofetil, azathioprine, tacrolimus, cyclosporine, or TNF-α inhibitors
- Women who are pregnant or nursing
- 7. How will **eligibility** be determined, and by whom?

Eligibility will be determined by the PI, [name], PhD and/or co-investigator [name]. Patients will be evaluated in person at a regular clinic appointment to determine if they meet inclusion criteria.

8. **Risks:** Describe the reasonably foreseeable risks, including risks to subject privacy, discomforts, or inconveniences associated with subjects participating in the research.

The risks associated with oral tofacitinib are listed below:

- Infections, including severe and opportunistic infections
- Viral reactivation
- Neutropenia
- Lymphopenia
- Anemia
- Malignancy
- Lymphoma
- Gastrointestinal perforation
- Headache
- Diarrhea
- Increased liver transaminases
- Increased creatinine
- Increased cholesterol

The above risks are very unlikely likely to occur with topical administration given what is known about transepidermal absorption and minimal surface area of application in this trial. Therefore, the only reasonably foreseeable risk is irritation at the site of application. There are no other known risks to the study.

9. **Minimizing Risks:** Describe the manner in which the above-mentioned risks will be minimized.

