## Minimal Risk DSMP

The principal investigator is responsible for monitoring the data, assuring protocol compliance, and conducting the safety reviews monthly. During the review process the principal investigator will evaluate whether the study should continue unchanged, require modification/amendment, or close to enrollment.

The principal investigator (monitor) or the Institutional Review Board (IRB) have the authority to stop or suspend the study or require modifications.

This protocol presents minimal risks to the subjects and Unanticipated Problems Involving Risks to Subjects or Others (UPIRSOs), including adverse events, are not anticipated. In the unlikely event that such events occur, Reportable Events (which are events that are serious or life-threatening and unanticipated (or anticipated but occurring with a greater frequency than expected) and possibly, probably, or definitely related) or Unanticipated Problems Involving Risks to Subjects or Others that may require a temporary or permanent interruption of study activities will be reported immediately (if possible), followed by a written report within 5 calendar days of the Principal Investigator becoming aware of the event to the IRB (using the appropriate forms from the website) and any appropriate funding and regulatory agencies. The investigator will apprise fellow investigators and study personnel of all UPIRSOs and adverse events that occur during the conduct of this research project as they are reviewed by the principal investigator. The protocol's research monitor, co-investigators and Pfizer will be informed of adverse events within 5 days of the event becoming known to the principal investigator.

11. Statistical Considerations: Describe the statistical analyses that support the study design.

This will be a pilot study that will be primarily observational in nature, and statistics will be purely descriptive. Pre-and post-treatment SALT scores will be compared for individual patients, and the mean change in score values from baseline will be described. Clinical photographs will be used to demonstrate presence or absence of hair regrowth.

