## SECTION VIII: PROTECTION OF RESEARCH SUBJECTS

#### Confidentiality & Security of Data:

a. What protected health information (medical information along with the HIPAA identifiers) about subjects will be collected and used for the research?

Name, age, gender, race, age of onset of alopecia areata and subsequent natural history (including episodes of regrowth and recurrence), prior therapies, comorbid conditions, percent scalp involvement of hair loss at initial presentation and follow-up visits (as measured via Severity of Alopecia Tool – SALT score), involvement of eyebrows, eyelashes and body hair, treatment including dose and duration, response to treatment, adverse effects

b. How will the research data be collected, recorded and stored? Laptop 1 with patient data in an Excel spreadsheet with a code identifier for each patient. The code identifiers will be stored separately on a different laptop computer. The laptops are encrypted with Yale security software.

- c. How will the digital data be stored? CD DVD Flash Drive Portable Hard Drive Secured Server Laptop Computer Desktop Computer Other
- d. What methods and procedures will be used to safeguard the confidentiality and security of the identifiable study data and the storage media indicated above during and after the subject's participation in the study?
  Study participants will be identified with a code number. Codes will be maintained in a separate file. All data will be kept in password-protected files on an encrypted Yale laptop. Do all portable devices contain encryption software? Xes No
  If no, see http://hipaa.yale.edu/guidance/policy.html
- e. What will be done with the data when the research is completed? Are there plans to destroy the identifiable data? If yes, describe how, by whom and when identifiers will be destroyed. If no, describe how the data and/or identifiers will be secured.

Code identifiers will be destroyed by [name] by deleting the file so that the data is deidentified. The de-identified data will be kept for two years.

f. Who will have access to the protected health information (such as the research sponsor, the investigator, the research staff, all research monitors, FDA, Yale Cancer Center Data and Safety Monitoring Committee (DSMC), SSC, etc.)? (please distinguish between PHI and de-identified data)

[name], [name], [name], YSM3, Yale Human Investigation Committee, Pfizer, Food and Drug Administration

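### The symptoms named for each visit are all systemic, so nothing explicitly prompts for burning, itching or pain where the ointment is applied, although local irritation is the one risk the protocol foresees

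*Combined protocol and SAP*

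**What the plan says.** Section V, item 3 (Research Plan) sets out three things to be done at each four-weekly visit. The first two are "Physical exam of the skin with special attention to presence or absence of hair growth, photographs of the skin". The third is a review of systems, given as a "complete review of systems (headache, dizziness, fever, cough, shortness of breath, nausea, vomiting, diarrhea) will be performed at each visit".

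Section V, item 8 (Risks) lists the known risks of oral tofacitinib, judges them very unlikely with topical use on a small area, and then states that "the only reasonably foreseeable risk is irritation at the site of application".

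Three other places bear on how a local reaction would be recorded or acted on:

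- The Research Plan changes the application frequency under a condition worded as "If a clinically significant adverse effect (lab abnormality or patient-reported adverse effect) is encountered".
- Section VIII, Confidentiality & Security of Data, item a, ends its list of collected data with "treatment including dose and duration, response to treatment, adverse effects".
- Section V, item 11 (Statistical Considerations) gives the photographs one purpose: "Clinical photographs will be used to demonstrate presence or absence of hair regrowth". It plans descriptive statistics on the SALT score and describes no safety summary.

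**The concern.** The visit list and the risk statement do not match. The protocol expects one kind of harm, at the skin where the ointment goes, yet the symptoms it names for systematic questioning all belong elsewhere. Symptoms that are asked about are reported more completely than symptoms left to the patient to raise. If the named list is followed literally, systemic complaints are elicited and local ones are not, and the two counts cannot be compared fairly. A report of little or no irritation could then reflect either good tolerability or the absence of a question.

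There is a second consequence. The Research Plan's rule on application frequency names laboratory abnormalities and patient reports as the routes by which an adverse effect comes to notice. Irritation is not a laboratory result. On the text, a symptom such as burning therefore reaches that rule only through the patient's report, and nothing tells staff to ask. The principal investigator's monthly safety review (Section V, item 10) can consider only what has been recorded.

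**Working it through.** The plan states no figure to reproduce: there is no expected irritation rate, no error rate and no derivation of the sample of 10. The check is a comparison of texts.

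**Step 1. Classify the named symptoms.** The review of systems names eight. Two are neurological (headache, dizziness), one is constitutional (fever), two are respiratory (cough, shortness of breath) and three are gastrointestinal (nausea, vomiting, diarrhea). That gives 2 + 1 + 2 + 3 = 8, with 0 of 8 local or cutaneous.

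**Step 2. Compare with the risk statement.** Section V, item 8 lists 13 risks of oral treatment. Headache and diarrhea are on that list by name, so 2 of the 8 prompted symptoms are risks the protocol considers very unlikely here. The risk it does foresee matches none of the eight.

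**Step 3. Look for capture elsewhere.**

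| Place | What it offers | Prompts for local symptoms? |
|---|---|---|
| Item 3, skin exam and photographs | Inspection at every visit, with hair growth as the stated emphasis | No; visible signs can be seen |
| Item 3, adverse-effect rule | Response to a laboratory abnormality or a patient report | No; depends on a report |
| Item 9, Minimizing Risks | Screening, time limit, monthly evaluation, labs, scalp only | No; irritation not mentioned |
| Item 10, monitoring plan | Monthly review by the principal investigator | No; uses what was recorded |
| Item 11, statistics | SALT change; photographs for regrowth | No safety summary described |
| Section VIII, item a | General adverse-effects entry | No; no local item or grade |

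**Step 4. Separate what is covered from what is not.** Redness and scaling present on the day of a visit can be found on the exam. Burning, itching and pain cannot be seen. Irritation that arises and settles within a four-week interval may leave nothing to see. These last two groups depend on the patient raising them, unless the review of systems is read as wider than its named items.

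**Step 5. Count the entries under the fix.** Two graded entries at baseline and at up to 6 four-weekly visits give 2 × 7 = 14 per patient at most, or 14 × 10 = 140 for the trial. The number is smaller for anyone who stops early or moves to treating all sites.

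**The case against.** The best reply is that the protocol asks for a *complete* review of systems. On that reading the bracketed symptoms are examples and skin is included. The visits take place in dermatology clinics, the skin is examined and photographed each time, and regrowth cannot be judged without looking at the treated scalp. Adverse effects are recorded without restriction to the eight symptoms, the principal investigator reviews safety monthly, and any clinically significant patient report can trigger action. The application form also asks for a summary in plain language, and item-level visit forms are not among the documents.

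Much of this stands. Visible irritation has a scheduled opportunity to be found, and a route exists for recording and acting on it. A reader might infer that patients will definitely not be asked about their scalp at any of up to 60 visits (10 patients × 6). The documents do not support that, because the wording is ambiguous and the visit forms are unseen.

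Asking about systemic symptoms is also reasonable. The background in Section V, item 2 justifies the topical route by the serious systemic effects it might avoid, and the systemic questions help check that. The list is incomplete rather than misdirected.

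What the reply does not supply is a prompt. None of the named items is cutaneous, the exam's only stated emphasis is hair growth, and a general adverse-effects entry records what is raised without raising it.

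**Conclusion.** The point holds in a limited form and is worth correcting before enrolment. It does not undermine the trial. The gap is the lack of an explicit, graded prompt for symptoms at the application site. It is not an absence of skin observation.

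Its size is 0 local items among 8 named, with no application-site question, grade or data field anywhere else in the protocol. This rests on reading the bracketed list as the content of the review of systems. If staff take *complete* to include skin, the gap narrows to an unstated, ungraded question.

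Two stronger conclusions are tempting and should not be drawn:

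- **An estimate of how many cases would be missed.** The documents give neither the frequency of irritation nor the share of patients who would volunteer it, so any number would be invented.
- **Local tolerability as the trial's main safety result.** The protocol does not rank its safety results, and its stated purpose is hair regrowth.

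What can be said is that, in a descriptive study of 10 patients, simple counts are all the safety evidence there will be. A count of irritation is hard to interpret if it is unclear whether anyone asked.

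**What to change.** In Section V, item 3, add to the baseline and each-visit assessment:

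- a prompted question on burning, itching or pain at the application site since the last visit (at baseline, current symptoms at the planned sites);
- a note of any visible irritation on the skin exam already scheduled;
- one overall grade (none, mild, moderate, severe) for treated scalp, and one for scalp not yet treated for as long as part of it remains untreated.

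In Section V, item 11, add that the number of patients with any irritation and each patient's worst grade will be reported descriptively.

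The second grade uses a feature the design already has. At the start, no more than half the patches or half the scalp is treated, so each patient carries an untreated area that helps separate ointment irritation from background scalp symptoms. That comparison ends when a patient extends treatment to all involved sites and cannot be recovered afterwards, and so it has to be recorded from baseline.

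The cost is about a minute and two graded entries per existing visit, held in the existing spreadsheet, with no added visit, test or staff. Reported irritation may look somewhat more frequent because it is elicited, and the report should say so. The change concerns data collection and description only. It leaves the treatment rules, sample size and SALT analysis as they are.
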